1. INTRODUCTION

This is an open-label, nonrandomized, Phase 1/2 study to determine the safety, tolerability, and efficacy of INCAGN01876 when given in combination with immune therapies. Phase 1 will consist of 2 parts. Dose Escalation (Part 1), will consist of a 3 + 3 + 3 design to determine the MTD [REDACTED]

[REDACTED] The Safety Expansion (Part 2) will further explore tolerated doses of INCAGN01876 from Part 1 given as a single-dose run-in followed by concomitant immune therapy. Subjects with advanced or metastatic cervical cancer, endometrial cancer, gastric cancer (including stomach and GEJ), esophageal cancer, HCC, melanoma (mucosal or cutaneous), Merkel cell carcinoma, mesothelioma, MSI-H solid tumors, NSCLC, ovarian cancer, SCCHN, SCLC, RCC, TNBC, and UC who have progressed after treatment with available therapies that are known to confer clinical benefit, who are intolerant to treatment, or who refuse standard of care will be enrolled in both parts of Phase 1.

The Phase 2 Dose Expansion will further evaluate the safety, tolerability, and efficacy of the recommended dose(s) of INCAGN01876 selected in Phase 1 when given in combination with immune therapies. Subjects with advanced or metastatic melanoma, RCC, and UC will be enrolled in Phase 2. Section 1 of the Protocol provides a detailed description of the study drug, target patient population, rationale for doses to be examined, and potential risks and benefits of treatment with INCAGN01876.

The purpose of this SAP is to provide details of the statistical analyses that have been outlined in the Study INCAGN 1876-202 Protocol. The scope of this plan includes the final analyses that are planned and will be executed by the Department of Biostatistics or designee. [REDACTED]

2. STUDY INFORMATION, OBJECTIVES, AND ENDPOINTS

2.1. Protocol and Case Report Form Version

This SAP is based on INCAGN 1876-202 Protocol Amendment 1 dated 24 AUG 2017 and CRFs approved 29 NOV 2017. Unless superseded by an amendment, this SAP will be effective for all subsequent Protocol amendments and eCRF versions.

2.2. Study Objectives

2.2.1. Primary Objectives

Phase 1

- To evaluate the safety, tolerability, and DLTs of INCAGN01876 in combination with immune therapies and to define the RP2D(s) of INCAGN01876 when given in combination with immune therapies.

Phase 2

- To evaluate the efficacy of INCAGN01876 when given in combination with immune therapies by assessing ORR or CRR per RECIST v1.1.

2.2.2. Secondary Objectives

Phase 1 and Phase 2

- To evaluate the efficacy of INCAGN01876 when given in combination with immune therapies by assessing ORR, DOR, DCR, duration of disease control, and PFS per RECIST v1.1 and mRECIST.
- To evaluate the efficacy of INCAGN01876 when given in combination with immune therapies with respect to 1-year and 2-year OS.
- To evaluate the safety and tolerability of INCAGN01876 when given in combination with immune therapies.

[REDACTED]

[REDACTED]

- [REDACTED]
- [REDACTED]
- [REDACTED]

2.3. Study Endpoints

2.3.1. Primary Endpoints

- Safety and tolerability will be assessed by monitoring frequency, duration, and severity of AEs (Phase 1).
- ORR, defined as the percentage of subjects having CR or PR, will be determined by investigator assessment of radiographic disease assessments per RECIST v1.1 (Phase 2).
- CRR, defined as the percentage of checkpoint inhibitor-naïve melanoma subjects who have a CR as determined by investigator assessment of radiographic disease assessments per RECIST v1.1 (Phase 2).

2.3.2. Secondary Endpoints

- ORR, defined as the percentage of subjects having CR or PR, will be determined by investigator assessment of radiographic disease assessments per RECIST v1.1 (Phase 1) and mRECIST (Phases 1 and 2).
- DCR, defined as the percentage of subjects having CR, PR, or SD, will be determined by investigator assessment of a radiographic disease assessments per RECIST v1.1 and mRECIST (Phases 1 and 2).
- DOR, defined as the time from the earliest date of disease response (CR or PR) until earliest date of disease progression or death due to any cause, if occurring sooner than progression, will be determined by investigator assessment of radiographic disease assessment per RECIST v1.1 and mRECIST (Phases 1 and 2).
- Duration of disease control (CR, PR, and SD) as measured from first report of SD or better until disease progression or death from any cause, if occurring sooner than progression, will be determined by investigator assessment of radiographic disease per RECIST v1.1 and mRECIST (Phases 1 and 2).
- PFS, defined as the time from the start of combination therapy until the earliest date of disease progression or death due to any cause, if occurring sooner than progression, as determined by investigator assessment of objective radiographic disease assessments per RECIST v1.1 and mRECIST (Phases 1 and 2).
- OS determined from the start of combination therapy until death due to any cause. Survival analyses will occur at 1 year, 2 years, and at the end of the study (Phases 1 and 2).
- Safety and tolerability will be assessed by monitoring frequency, duration, and severity of AEs (Phase 2).

[REDACTED]

- [REDACTED]
- [REDACTED]
- [REDACTED]

3. STUDY DESIGN

[figure not shown]
3.1. Overall Study Design

This is an open-label, nonrandomized, Phase 1/2 study to determine the safety, tolerability, and efficacy of INCAGN01876 when given in combination with immune therapies. Phase 1 will consist of 2 parts. Dose Escalation (Part 1) will consist of a 3 + 3 + 3 design to determine the MTD, [REDACTED]

[REDACTED] The Safety Expansion (Part 2) will further explore tolerated doses of INCAGN01876 from Part 1 given as a single-dose run-in followed by concomitant immune therapy. Subjects with advanced or metastatic cervical cancer, endometrial cancer, gastric cancer (including stomach and GEJ), esophageal cancer, HCC, melanoma (mucosal or cutaneous), Merkel cell carcinoma, mesothelioma, MSI-H solid tumors, NSCLC, ovarian cancer, SCCHN, SCLC, RCC, TNBC, and UC who have progressed after treatment with available therapies that are known to confer clinical benefit, who are intolerant to treatment, or who refuse standard of care will be enrolled in both parts of Phase 1.

The Phase 2 Dose Expansion will further evaluate the safety, tolerability, and efficacy of the recommended dose(s) of INCAGN01876 selected in Phase 1 when given in combination with immune therapies. Subjects with advanced or metastatic melanoma, RCC, and UC will be enrolled in Phase 2. See [Figure 1](#) for overall study design.

Figure 1: Overall Study Design

3.1.1. Phase 1 – Dose Escalation (Part 1)

A minimum of 3 evaluable subjects will be enrolled in Treatment Group A (see Table 2), beginning with INCAGN01876 Dose Cohort 1 (1.0 mg/kg; starting dose; see Table 1). A higher starting dose of INCAGN01876 may be used if safety data are available from the monotherapy study (INCAGN 1876-101), but it will not exceed 1 dose level below the highest tolerated dose of INCAGN01876 monotherapy. If a higher dose is used, the dose will be communicated to investigational sites with an administrative letter. The first 3 evaluable subjects enrolled within an INCAGN01876 dose cohort will be observed for a minimum of 28 days before the next dose cohort begins enrollment. If 0 DLTs occur in a cohort of 3 evaluable subjects, a new cohort of 3 evaluable subjects will be treated at the next higher dose level. If 1 of 3 evaluable subjects experiences a DLT, that cohort will be expanded to 6 evaluable subjects. If 1 of 6 evaluable subjects experiences a DLT, a new cohort of 3 evaluable subjects will be treated at the next higher dose level. If 2 of 6 evaluable subjects experience a DLT, that cohort will be expanded to 9 evaluable subjects. If ≥ 2 of 3, 3 of 6, or 3 of 9 evaluable subjects experience DLTs within a cohort, then that dose level will be determined to have exceeded the MTD, and the previous dose level will be considered the MTD. If only 3 evaluable subjects were treated at the MTD, then a minimum of 3 additional evaluable subjects will be enrolled before this dose is administered in Phase 2 of the study.

Additional subjects will be enrolled in a dose cohort to achieve the minimum of 3 evaluable subjects. Subjects who drop out for reasons other than a DLT (eg, events clearly associated with the underlying disease, disease progression, concomitant medication, or comorbidity) during the DLT observation period will result in the subjects being nonevaluable and replaced. Dose modifications should not be made during the DLT observation period without discussion with the medical monitor. The doses of INCAGN01876 to be evaluated in each treatment group are summarized in [Table 1](#).

Table 1: INCAGN01876 Dose Cohorts

Dose Cohort	Dose of INCAGN01876
-1	0.3 mg/kg
1 (Starting Dose)	1.0 mg/kg^a
2	3.0 mg/kg
3	5.0 mg/kg
4	10.0 mg/kg

^a A higher starting dose of INCAGN01876 [REDACTED] was used based on safety data from the monotherapy study (INCAGN 1876-101), but it did not exceed 1 dose level below the highest tolerated dose of INCAGN01876 monotherapy. The higher dose was communicated to investigational sites with an administrative letter.

3.1.1.1. Treatment Group A: INCAGN01876 + Pembrolizumab

Treatment Group A will treat subjects with INCAGN01876 at the assigned dose level administered Q3W in combination with 200 mg of pembrolizumab administered Q3W and [REDACTED] epacadostat administered orally BID (see [Table 2](#)). **There will be a waiting period of 48 hours between dose administration of the first subject and second subject of each dosing cohort.** The first 3 evaluable subjects enrolled within a cohort will be observed for 28 days before the next cohort begins enrollment. Dose escalation of INCAGN01876 will proceed as outlined in [Table 1](#) until the MTD [REDACTED] of INCAGN01876 in combination with pembrolizumab and epacadostat is determined. Subjects must receive at least 1 dose of the cohort-specified dose of INCAGN01876, 1 dose of pembrolizumab, and at least 75% of planned doses of epacadostat (42 doses) or have had a DLT during the DLT observation period to be considered evaluable.

Table 2: Phase 1 Dose Escalation of Treatment Group A

[figure not shown]
Treatment Group A	INCAGN01876 Concurrent Dose Administration	Pembrolizumab	Epacadostat
		See INCAGN01876 dose cohorts (Table 1) Q3W starting at Cycle 1	200 mg Q3W starting at Cycle 1

3.1.2. Phase 1 – Safety Expansion (Part 2)

Once an INCAGN01876 dose cohort in Treatment Group A is deemed tolerable (ie, no DLTs or unacceptable toxicities were observed within the defined DLT observation period of at least 28 days), up to 6 evaluable subjects will be enrolled in Treatment Group B at the same dose of INCAGN01876 (see Figure 2). For example, if 3.0 mg/kg of INCAGN01876 is tolerated in Treatment Group A, then 3.0 mg/kg will be explored in up to 6 evaluable subjects in Treatment Group B. Doses of INCAGN01876 in Treatment Group B will be escalated in parallel to those explored in Treatment Group A, but will not exceed the MTD of INCAGN01876 established in Treatment Group A. Alternate dose administration schedules may also be explored depending on █ safety results. The sponsor may elect to prioritize (or deprioritize) enrollment to specific dose cohorts based on emerging safety or efficacy data in collaboration with investigational sites.

If the cumulative incidence of Grade 3 or higher INCAGN01876-related AEs occurs in > 40% of subjects in a particular treatment group, then further enrollment will be interrupted until the sponsor, investigators, and regulatory authorities (if applicable) determine the appropriate course of action (eg, lower the dose of INCAGN01876, change dose frequency, etc).

Figure 2: Phase 1 Safety Expansion (Part 2)

3.1.2.1. Treatment Group B: INCAGN01876 + Epacadostat Run-In Followed by INCAGN01876 + Pembrolizumab + Epacadostat

Treatment Group B will treat subjects with a single-dose run-in of INCAGN01876 at the assigned dose level in combination with [REDACTED] epacadostat administered orally BID, followed by the combination of INCAGN01876 Q3W, 200 mg of pembrolizumab Q3W starting at Cycle 2, and [REDACTED] epacadostat administered orally BID (see Table 3).

Table 3: Phase 1 Safety Expansion of Treatment Group B

Treatment Group B	INCAGN01876 Run-In Followed by Concurrent Dose Administration	Pembrolizumab	Epacadostat
	See INCAGN01876 dose cohorts (Table 1) Q3W starting at Cycle 1	200 mg Q3W starting at Cycle 2	[REDACTED] starting at Cycle 1

3.1.3. Phase 2 – Dose Expansion

Phase 2 will further evaluate the safety, tolerability, efficacy, [REDACTED] in subjects with advanced or metastatic melanoma, RCC, and UC. Additional tumor-specific cohorts may be added, by protocol amendment, based on emerging data.

Biopsy cohorts will be added at specific institutions for each treatment group (C and D), where serial mandatory pretreatment and on-treatment biopsies will be collected to evaluate changes in the tumor microenvironment. Approximately 15 evaluable subjects who have tumor lesions that are amenable to percutaneous biopsy will be enrolled in each biopsy cohort. The biopsy-specific cohorts will be limited to subjects with melanoma (mucosal or cutaneous), RCC, and UC (refer to the Protocol, Section 7.10.4).

The Phase 2 dose expansion treatment groups and tumor-specific cohorts for each treatment group are outlined in Table 4. A Simon 2-stage design will be used with a stopping rule to allow for early termination of a particular cohort at the end of Stage 1 if there are insufficient responses observed (Simon 1989). The approximate number of subjects for Stage 1 and Stage 2 for each treatment group and tumor type is described in Table 6. Enrollment in Phase 2 will begin when the MTD [REDACTED] of INCAGN01876 for a given treatment group in Phase 1 has been determined.

Table 4: Phase 2 Dose Expansion Treatment Groups

Dose Expansion Treatment Groups				
Treatment Group C	INCAGN01876 Concurrent Dose Administration	Pembrolizumab	Epacadostat	Tumor Cohorts
	MTD [REDACTED] of Treatment Group A Q3W starting at Cycle 1	200 mg Q3W starting at Cycle 1	[REDACTED] starting at Cycle 1	Cohort 1 – Biopsy Cohort 2 – Melanoma Cohort 3 – RCC Cohort 4 – UC

The diagram for Treatment Group C shows a timeline starting at Cycle 1. Pembrolizumab (Pembro) is administered every 3 weeks, indicated by downward arrows. Epacadostat is administered continuously, shown as a long horizontal arrow. GTR is administered every 3 weeks, indicated by upward arrows.
				
Treatment Group D	INCAGN01876 Run-In Followed by Concurrent Dose Administration	Pembrolizumab	Epacadostat	Tumor Cohorts
	MTD [REDACTED] of Treatment Group A Q3W starting at Cycle 1	200 mg Q3W starting at Cycle 2	[REDACTED] starting at Cycle 1	Cohort 1 – Biopsy Cohort 2 – Melanoma Cohort 3 – RCC Cohort 4 – UC

The diagram for Treatment Group D shows a timeline starting at Cycle 1. Epacadostat is administered continuously from Cycle 1, shown as a long horizontal arrow. GTR is administered every 3 weeks starting at Cycle 1, indicated by upward arrows. Pembrolizumab (Pembro) is administered every 3 weeks starting at Cycle 2, indicated by downward arrows.
				

In Phase 2 of the study, toxicities will continue to be monitored. If the cumulative incidence of Grade 3 or higher INCAGN01876-related AEs occurs in > 40% of subjects in a particular treatment group after 6 subjects have been enrolled, then further enrollment in that treatment group will be interrupted until the sponsor, investigators, and regulatory authorities (if applicable) determine the appropriate course of action (eg, lower the dose of INCAGN01876, change dose frequency, etc). If a treatment group is discontinued due to toxicity, it may be re-initiated at a previously tested lower dose level and/or alternate dosing schedule. All AEs, regardless of the time of occurrence on study, may be considered for DLT determination purposes.

3.2. Randomization

Not applicable.

3.3. Control of Type I Error

For the primary efficacy endpoints, the 1-sided Type I error will be controlled at 0.05 for each individual cohort expansion. Note that this level of significance does not account for the multiple expansion cohorts. For other endpoints, CIs will be reported at a 95% confidence level.

3.4. Sample Size Considerations

3.4.1. Sample Size in Phase 1 Part 1

The primary objective of Phase 1 of the study is to evaluate the safety, tolerability, and DLTs of INCAGN01876 in combination with immune therapies and to determine the RP2Ds of INCAGN01876 when given in combination with immune therapies. The total number of subjects will depend on the number of dose levels tested before the recommended dose(s) are established. Dose escalation will follow the 3 + 3 + 3 design algorithm (see Section 3.1.1). Based on this algorithm, a minimum of 3 evaluable subjects will be enrolled in each cohort with a maximum of 9 evaluable subjects in each cohort.

The probabilities of dose escalation from a given dose level for the various DLT rates are provided in [Table 5](#).

Table 5: Probability of Dose Escalation for Various Dose-Limiting Toxicity Rates

True DLT Rate	Probability of Dose Escalation
20%	78.4%
30%	56.1%
40%	35.0%
50%	18.9%
60%	8.8%

For example, if the true DLT rate is 50% at a given dose level, there is an 18.9% chance that the dose would be escalated. Further, if the true DLT rate is 20%, there is a 78.4% chance that the dose would be escalated. If the MTD is not determined at the highest dose level tested during the study, then the MTD is at or above the highest dose level. The MTD is below the lowest dose level of INCAGN01876 if the Cohort 1 dose is not well-tolerated.

3.4.2. Sample Size in Phase 1 Part 2

Once an INCAGN01876 dose cohort in Treatment Group A is deemed tolerable, up to 6 evaluable subjects will be enrolled in Treatment Group B at the same dose of INCAGN01876. For example, if 3.0 mg/kg of INCAGN01876 is tolerated in Treatment Group A, then 3.0 mg/kg will be explored in up to 6 evaluable subjects in Treatment Group B.

3.4.3. Sample Size for Phase 2

Phase 2 will further evaluate the safety, tolerability, preliminary efficacy, [REDACTED] of the immune therapy combinations as part of dose expansion cohorts in Treatment Groups C and D. In Phase 2, a Simon 2-stage design will be run for each tumor type within a given treatment group.

The sample size for each tumor type within a given treatment group will be guided by the Simon 2-stage design. The planned Simon 2-stage designs are summarized in Table 6. Each Simon 2-stage design will have a stopping rule to allow early termination of a particular cohort at the end of Stage 1 if there are insufficient responses observed, while enrolling enough subjects to predict possible target responses worthy of cohort expansion and potentially further evaluation in future studies.

The individual Simon 2-stage designs run for each tumor type within each treatment group will have design parameters that are determined by historical response rates. For the RCC and UC cohorts, the insufficient response rates are obtained from historical data, and the Simon 2-stage designs allowing early termination are based on ORR. For the melanoma cohort, the insufficient response rate is obtained from historical data, and the primary endpoint for the Simon 2-stage design allows for early termination based on CRR. The same Simon 2-stage design parameters will be used for the alternative dosing sequences represented by Treatment Groups C and D in the same tumor type. For example, the RCC cohorts in Treatment Groups C and D will use the same Simon 2-stage parameters.

In order to determine whether the target response rate (p_1) is likely, an initial number of evaluable subjects (n_1 subjects) will be treated at the MTD [REDACTED] and schedule of INCAGN01876 within the corresponding tumor type and treatment group and will be enrolled in a cohort (Stage 1). If there are r_1 or fewer responses in the cohort, it will be concluded that the true response rate is unlikely to be greater than or equal to the target rate, and no more subjects will be enrolled in that tumor type cohort for that treatment group in Stage 2. In the cohorts in which greater than r_1 responses are observed among the Stage 1 subjects, n_2 additional evaluable subjects will be treated in Stage 2 to estimate the response rate. At the end of Stage 2, if $\leq r$ subjects have responded among the n evaluable subjects, the triplet combination dosing sequence will be declared nonpromising for that cohort. In other words, after the study is finished, if there is a sufficient number of responses in the 2 stages combined, the triplet combination dosing sequence is considered promising; otherwise it is considered nonpromising.

The detailed calculations for each tumor-specific cohort are based on a 1-sided Type I error of 0.05 and power of 85%. The individual p_0 and p_1 values for the tumor types are listed in Table 6.

A second approach to determining whether the treatment is active across the cohorts will use an integrated Bayesian futility analysis of tumor and dosing strategies specific to Treatment Groups C and D.

Formal quarterly safety reviews will be conducted to review efficacy and safety data with the obligation to hold a safety review meeting every 6 months.

Table 6: Planned Simon 2-Stage Designs for Phase 2

Indication	Combination	r_1	n_1	r	n_2	n	p_0	p_1
Melanoma (CRR)	GITR + Pembro + Epcadostat	6	21	18	31	52	26%	45%
RCC (ORR)	GITR + Pembro + Epcadostat	8	19	25	31	50	40%	60%
UC (ORR)	GITR + Pembro + Epcadostat	3	10	14	24	34	30%	55%

3.5. Schedule of Assessments

See Protocol Amendment 1 dated 24 AUG 2017 for a full description of all study procedures and assessment schedules for this study.

4. DATA HANDLING DEFINITIONS AND CONVENTIONS

4.1. Scheduled Study Evaluations and Study Periods

4.1.1. Day 1

Day 1 is the date that the first dose of study drug (INCAGN01876, pembrolizumab, or epcadostat) is administered to the subjects.

4.1.2. Study Day

If a visit/reporting date is on or after Day 1, then the study day at the visit/reporting date will be calculated as

$$\text{Day \#} = (\text{Visit/Reporting Date} - \text{Day 1 date} + 1).$$

If the visit/reporting date is before Day 1, then the study day at the visit/reporting date will be calculated as

$$\text{Day \#} = (\text{Visit/Reporting Date} - \text{Day 1 date}).$$

A study day of -1 indicates 1 day before Day 1.

4.1.3. Baseline Value

Baseline is the last nonmissing measurement obtained before the first administration of INCAGN01876, pembrolizumab, or epacadostat, unless otherwise defined.

When scheduled assessments and unscheduled assessments occur on the same day and time of the assessment or time of first dose is not available, use the following convention to determine baseline:

- If both a scheduled and an unscheduled visit are available on the day of the first dose and the time is missing, use the scheduled assessment as baseline.
- If all scheduled assessments are missing on the day of the first dose and an unscheduled assessment is available, use the unscheduled assessment as baseline.

4.1.4. Handling of Missing and Incomplete Data

In general, values for missing data will not be imputed unless methods for handling missing data are specified in this section or relevant sections.

Partial disease/cancer diagnosis date will be handled as follows:

- If only the day is missing, then the imputed day will be the first of the month.
- If both the month and day are missing, then the imputed day and month will be 01 JAN.
- No imputation will be done if the date is completely missing.

Missing or partial date of last dose will be handled as follows:

- If only the day is missing, then the imputed date of the last dose will be the earlier date of the first day of the month or the date that the subject discontinued treatment.
- Otherwise, the date that the subject discontinued treatment will be used as the date of the last dose.

For relevant efficacy endpoints, partial death date will be imputed as follows:

- If mmyyyy for the last contact date = mmyyyy for the death date, then the death date will be set to the day after the last contact date.
- If mmyyyy for the last contact date < mmyyyy for the death date, then the death date will be set to the first day of the death month.
- Otherwise, the partial death date will not be imputed.

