5.2.2. Epacadostat

5.2.2.1. Description and Administration

Epacadostat will be self-administered orally [REDACTED] without regard to food. Doses will be taken in the morning and evening, approximately 12 hours apart. If a dose is missed by more than 4 hours, then the dose should be skipped, and the next dose should be taken at the usual time.

For subjects enrolled in Phase 1 and Phase 2, Treatment Groups A through D, epacadostat will begin on Cycle 1 Day 1 and will be self-administered continuously, [REDACTED] (see [Table 18](#)). [REDACTED] epacadostat will be administered at the clinic and should be taken before the INCAGN01876 infusion. Treatment will continue as long as subjects are deriving benefit and have not met any of the Protocol-defined conditions for treatment withdrawal (see [Section 5.5](#)) or for up to 24 months from the first dose of study treatment, whichever occurs first.

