6.4. Exposure

6.4.1. Exposure for INCAGN01876

For subjects in the FAS population, exposure to INCAGN01876 will be summarized descriptively as the following:

- **Total number of infusions:** Total number of infusions per subject with a nonzero dose of INCAGN01876.

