6.4.2. Exposure for Pembrolizumab

The exposure for pembrolizumab will be summarized the same as that for INCAGN01876 in Section 6.4.1.

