6.4.3. Exposure for Epacadostat

For subjects in the FAS population, exposure to epacadostat will be summarized descriptively as the following:

- **Duration of treatment (days):** Date of last dose of epacadostat – date of first dose of epacadostat + 1.

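### When only the day of the last dose is missing, the SAP rule always gives the first of the month, so epacadostat duration is understated and can be zero or negative

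*SAP*

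**What the plan says.** SAP 4.1.4 has two rules for a missing or partial last-dose date. With only the day missing, the imputed date is "the earlier date of the first day of the month or the date that the subject discontinued treatment". For every other case the SAP says: "Otherwise, the date that the subject discontinued treatment will be used as the date of the last dose". Neither rule ties the result to the date of first dose.

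SAP 6.4.3 defines epacadostat duration of treatment as "Date of last dose of epacadostat – date of first dose of epacadostat + 1". It is summarized in Table 3.1.3 of SAP Appendix A, and SAP 5.1 lists mean, median, minimum and maximum among the standard descriptive statistics.

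The other two drugs are handled differently. INCAGN01876 exposure is "Total number of infusions per subject with a nonzero dose of INCAGN01876" (SAP 6.4.1), and for pembrolizumab SAP 6.4.2 says: "The exposure for pembrolizumab will be summarized the same as that for INCAGN01876". Neither measure uses a last-dose date.

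**The concern.** A rule that takes the earlier of two dates is useful only if either date can be the earlier one. Here the second is a discontinuation date, which normally follows the last dose, so it cannot precede the start of the last-dose month. A clause that never operates looks like a drafting slip rather than a deliberate conservative choice.

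The rest of SAP 4.1.4 points the same way. If the month is also missing, the discontinuation date is used, so a less complete record gets a later and more plausible date than one with a known month. The partial death-date rule protects the order of events: if the month matches the last contact, death is placed the day after that contact. The last-dose rule has no such protection.

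At stake is whether Table 3.1.3 shows shortened or impossible treatment durations. Epacadostat is the drug for which an unknown last day is most plausible, because it is taken at home: per Protocol 5.2.2.1, "epacadostat will begin on Cycle 1 Day 1 and will be self-administered continuously". That a site may not know the day is an inference, not a statement in the documents. SAP 10.1.1.2 reports limited enrolment in Treatment Group C and none in Groups B and D, so a single bad value would move the mean and the minimum.

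**Working it through.** The documents give no figure for this rule, so there is nothing to reproduce. The inputs are the two imputation rules in SAP 4.1.4 and the duration formula in SAP 6.4.3. Calendar year 2018 and the example dates are assumptions for illustration.

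Let F be the first dose, L the true last dose, D the discontinuation date, and M1 the first day of the month of L.

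**1. Which date does the rule return?** L lies in its own month, so L ≥ M1. If D ≥ L, then D ≥ M1 and min(M1, D) = M1. As a check, every last-dose date in 2018 was paired with a discontinuation 0 to 60 days later: 365 × 61 = 22,265 pairs. The rule returned the first of the month in all of them.

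**2. Size of the understatement.** It equals L − M1, that is, the day of the month minus 1, so it runs from 0 (true last dose on the 1st) to 30. For a uniform day in a month of n days the mean is (n − 1)/2: 13.5 for n = 28, 14.5 for n = 30 and 15 for n = 31. Over 2018 it is 14.7 days.

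**3. First and last dose in the same month.** If dosing began on day d, duration = 1 − d + 1 = 2 − d.

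| d | Duration (days) |
|---|---|
| 1 | 1 |
| 2 | 0 |
| 3 | -1 |
| 12 | -10 |
| 15 | -13 |
| 31 | -29 |

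Only a start on the 1st gives a positive value. Zero or negative results follow from 27 of 28 start days in a 28-day month and 30 of 31 in a 31-day month.

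**4. The rules side by side.** F = 5 March, L = 26 March, D = 28 March:

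| Rule | Last dose used | Duration (days) |
|---|---|---|
| True date | 26 March | 26 − 5 + 1 = 22 |
| SAP, day missing | 1 March | 1 − 5 + 1 = -3 |
| SAP, month also missing | 28 March | 28 − 5 + 1 = 24 |
| SAP date, floored at first dose | 5 March | 1 |
| Earlier of month-end and D, floored at first dose | 28 March | 24 |

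If dosing began on 10 January instead, the true duration is 76 days. The SAP rule gives 51 and the month-end rule gives 78.

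**5. Error of the alternative.** The month-end rule overstates by min(D, month-end) − L. Over 2018 the mean overstatement is 0 days if D = L, 1.9 if D is 2 days later, 6.1 at 7 days, 10.5 at 14 days and 13.4 at 21 days. It cannot exceed the distance to month-end, which is at most 30 days and by symmetry also averages 14.7. So with uniform days its mean error is no larger than that of the SAP rule, and it is much smaller when discontinuation soon follows the last dose.

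**The case against.** The best counter-argument concerns reach.

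- **The rule is a fallback.** Protocol 5.5.2 requires the last-dose date in the eCRF and an end-of-treatment visit. Protocol 5.3.1 requires tablet accountability, with compliance reviewed at each visit. Cycle 1 has visits on Days 1, 8 and 15 (Protocol Table 11), so a wholly unknown day is less likely in subjects who stopped within weeks, the group in which impossible values arise. This stands: the number of partial dates is not given and may be zero.
- **A reader might infer that every imputed last-dose date is biased downward.** The documents do not support that. The second rule imputes the discontinuation date, which on the same premise is on or after the true last dose, so any error there is zero or upward.
- **A reader might infer that exposure to all three drugs, or the efficacy and safety results, are affected.** In the public text they are not. The antibodies are summarized by infusion counts. The response rate (SAP 7.2.1) does not use the date, the treatment-emergent definition (SAP 8.2.1) has no cut-off tied to last dose, and the adverse event summaries (SAP 8.2.4) are numbers and percentages of subjects. SAP section 9 cancels the interim analyses.
- **Discontinuation need not follow the last dose.** Protocol 6.2 ends treatment at the investigator's decision, and a self-administered tablet could be taken afterwards, across a month-end. The discontinuation option would then operate, but it would return a date before the month in which the last dose is recorded. This is a narrow exception and does not help the rule.
- **The first of the month is a house convention.** The SAP uses it for partial diagnosis dates and in one branch for death dates. Consistency is a fair reason, but it does not explain a discontinuation clause that has no effect or the absence of a floor.

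**Conclusion.** The defect is real and small. Provided discontinuation is on or after the last dose, the day-missing branch of SAP 4.1.4 always returns the first of the month. In that branch alone, epacadostat duration is understated by 0 to 30 days, with a mean of about 15 if the true day is uniform. It is zero or negative when first and last dose share a month and dosing began after the 1st; a start on the 1st gives 1 day.

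The effect is confined to one descriptive variable in the synoptic report of a study that stopped enrolling early. It would be tempting to conclude that the reported exposure is wrong. The documents do not show that, because they do not say whether any last-dose date lacks its day. What they do show is that the rule, applied as written, can generate impossible values. No efficacy or safety conclusion in the public text rests on it.

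**What to change.** In SAP 4.1.4, replace the day-missing rule with: the earlier of the last day of the month and the date of treatment discontinuation (or death), and never earlier than the date of first dose.

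The floor at first dose is the essential part, since it alone removes zero and negative durations. The month-end cap makes the discontinuation date operative and brings this branch into line with the rule for less complete dates. Its downside should be stated in the SAP: duration may be overstated, up to the discontinuation date or month-end.

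The cost is one line in the SAP and one line of derivation code, with no change to data collection. If no epacadostat last-dose date lacks its day, no reported duration changes.
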